Secondary Aim 1: Test the efficacy of EnCoRE in producing positive changes at PT and FU on a second measure of social/community functioning (UPSA-B). Hypothesis 3 (H3): Veterans exposed to EnCoRE will have higher mean scores than controls at post-treatment and at FU on the UPSA-B total score.

Secondary Aim 2: Test the efficacy of EnCoRE in producing positive changes at PT and FU on mental health recovery. Hypothesis 4 (H4). Veterans exposed to EnCoRE will have higher mean ratings on the MARS than control at PT and FU. Analysis models for H4 will be parallel to those for H1.

Secondary Aim 3: Assess the modifying effect of covariates on the effectiveness of EnCoRE including general cognitive ability and psychotic symptoms. Hypothesis 5 (H5): General cognitive ability and symptoms of psychosis will not impact the effectiveness of the intervention

for negative symptoms and community functioning at PT and FU (See analysis below for H6). Hypothesis 6 (H6): Greater ratings of consumer participation in and satisfaction with the intervention will be associated with better PT and FU outcomes. For each of the potential modifiers in H5 and H6, we will re-fit the primary analysis model for PT outcomes after adding two terms, the potential modifier and the interaction term between the treatment condition indicator (Tx condition) and the potential modifier. The variable will be a modifier if the coefficient for the interaction term is statistically significant ( $p$ -value<.05). A similar model will be used to assess modification at FU but there will be additional interaction terms with time (including 3-way interaction time\*treatment condition\*modifier), in order to estimate modifying effects at FU (i.e. separate effects at FU vs. PT).

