#### Sample Size Considerations

We have powered this RCT for primary hypotheses 1 and 2 of Specific Aim 2 (two outcome measures). We consider the tests for the FU assessment as secondary. A medium effect size at PT (e.g. Cohen's  $d$  = .50) would generally represent a minimum clinically important difference. For example, for the primary outcome in H1, the CAINS Affective-Motivational Deficit Subscale (average rating range: 0–4), we know that  $d$ =.50 represents a .36 point difference in means between EnCoRE and control at PT which is slightly more than 1/3 of the distance

between anchor points (0=No impairment, 1=Mild deficit, 2=Moderate deficit, 3=Moderately Severe deficit, 4=Severe deficit). Because we are testing 2 hypotheses under Specific Aim 2, we specified the alpha level=.05/2=.025 for the sample size calculation. Power was set =.80. We expect 15% attrition at PT. For these specifications and under the primary analysis model, we would need a sample size of N=92 when the correlation between baseline and post-treatment outcome measure = .70. Although, setting this correlation to .70 is reasonable, this correlation could plausibly be lower, requiring the sample size to be greater. Therefore, we reset this correlation to be .63, and found that a sample size of N = 108 would then be required. Calculations were performed assuming a repeated measures design using the Sampsi command in Stata version 8.

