Document Type: Statistical Analysis Plan

Document Date: April 6, 2021

Outcomes Table

Type of Outcome	Description of Measure	Scale or Score	Time period
Primary	Clinical Assessment Interview for Negative Symptoms (CAINS, Kring et al., 2013), a 13-item measure of negative symptoms that includes two subscales: expression (4 items) and motivation and pleasure (9 items).	CAINS Motivation and Pleasure Scale (CAINS-MAP)	Baseline-12 weeks
Primary	Clinical Assessment Interview for Negative Symptoms (CAINS, Kring et al., 2013), a 13-item measure of negative symptoms that includes two subscales: expression (4 items) and motivation and pleasure (9 items).	CAINS Motivation and Pleasure Scale (CAINS-MAP)	Baseline-24 weeks
Primary	Social Functioning Scale (SFS, Birchwood et al., 1990) measures engagement in social activities through assessment of seven domains: Social Engagement/Withdrawal, Interpersonal Communication, Prosocial, Independence-Performance, Recreation, Independence-Competence, and Employment. In the present analysis, we used a total score for the SFS including all subscales except the employment subscale.	Social Functioning Scale	Baseline-12 weeks
Primary	Social Functioning Scale (SFS, Birchwood et al., 1990) measures engagement in social activities through assessment of seven domains: Social Engagement/Withdrawal, Interpersonal Communication, Prosocial, Independence-Performance, Recreation, Independence-Competence, and Employment. In the present analysis, we used a total score for the SFS including all subscales except the employment subscale.	Social Functioning Scale	Baseline-24 weeks
Secondary	Clinical Assessment Interview for Negative Symptoms (CAINS, Kring et al., 2013), a 13-item measure of negative symptoms that includes two subscales: expression (4 items) and motivation and pleasure (9 items).	CAINS Social Motivation and Pleasure Scale (CAINS-MAP)	Baseline-12 weeks

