
Statistical Test of Hypothesis: The analysis of the primary outcomes utilized a mixed effects model accounting for a random therapy group effects and the analysis included all available data at baseline, post-treatment, and follow-up time-points. Error terms across time points were assumed correlated with unstructured correlation matrix. To test time-specific hypotheses, terms in the mean model included separate indicators for post-treatment and follow-up time points, and interaction terms between these indicators and condition. Based on randomization to treatment condition, the model assumed no differences at baseline, i.e. any differences were assumed to be due to random sampling error. All continuous outcome scales were checked for skew, and an appropriate transformation was applied as needed. Statistical significance was defined as $p \leq .05$. All analyses were performed using SAS version 9.4. In moderator analyses we examined whether treatment effects on the primary outcomes (CAINS MAP, SFS) differed according to baseline dysfunctional attitudes measured by the DAS and SARA-Q. We also examined whether baseline negative symptoms (CAINS MAP) modified treatment effects for the SFS. Each moderator variable was dichotomized at the median. In separate models, the moderator and interaction terms with the moderator were added to the primary linear mixed effects models to test whether treatment effects at post-treatment and follow-up time points differed for those above versus below the median.

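### The SAP cuts each baseline moderator scale at the sample median, without a rationale or a tie rule, which loses information if moderation is graded

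*SAP*

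**What the plan says.** The SAP, under Statistical Test of Hypothesis, describes moderator analyses of the two primary outcomes, CAINS-MAP and SFS. It asks whether treatment effects "differed according to baseline dysfunctional attitudes measured by the DAS and SARA-Q", and adds: "We also examined whether baseline negative symptoms (CAINS MAP) modified treatment effects for the SFS". For the coding it says: "Each moderator variable was dichotomized at the median". The moderator and its interactions are then added to the primary mixed model, to test whether effects at post-treatment and follow-up "differed for those above versus below the median".

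The SAP gives no rationale for the cut, no analysis with the moderator left as a score, and no statement of which half takes a score equal to the median.

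The protocol mentions no cut-point. Its one written modifier model (section 5.6, Secondary Aim 3) adds the modifier and its product with treatment. That model is introduced with "For each of the potential modifiers in H5 and H6" and does not say how a modifier is coded. Section 5.1 names attitudes and beliefs among the possible moderators, and section 5.6 promises a check of baseline severity by treatment. Neither states a coding.

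**The concern.** DAS, SARA-Q and CAINS-MAP are scale scores. A median split treats two patients just either side of the cut as different, and treats everyone within a half as the same. If benefit rises or falls gradually with the score, most of what the data say about that gradient lies in the spread within the halves, and the split does not use it.

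Two things are at stake. Graded moderation is more likely to be missed, in a trial sized only for main effects. The result also depends on where this sample's median happens to fall and on a tie rule that the reader cannot see, so the split cannot be reproduced exactly from the SAP.

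**Working it through.** **Inputs.** From the protocol, Sample Size Considerations: d = .50, alpha = .025, power = .80, baseline to post-treatment correlation .63 (alternative .70), 15% attrition at post-treatment. From the SAP: moderator tests at .05. Not in the documents, so assumed: moderator shape, interaction size and form, two-sided tests.

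**1. The plan's own figure.** Patients per arm = 2 × [√(1 − r²) × (z₀.₉₈₇₅ + z₀.₈₀) / d]².
- r = .63: √(1 − .63²) = .777, giving 45.9, so 46 per arm and 92 evaluable; 92/.85 = 108.2. Without rounding up, the total is 107.9. This reproduces 108.
- r = .70: 39 per arm, 78 evaluable; 78/.85 = 91.8. This reproduces the plan's alternative total of 92.

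Below, 92 always means the evaluable patients out of 108.

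**2. Information kept by the split.** Under linear moderation this is the squared correlation between the score and the indicator that it exceeds its median.

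| Assumed shape | Kept | Lost | 92 patients act like |
|---|---|---|---|
| Normal | 2/π = .637 | 36% | 59 |
| Uniform | .75 | 25% | 69 |
| Exponential | (ln 2)² = .480 | 52% | 44 |

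**3. Power under linear moderation, normal moderator.** The model is an ANCOVA with baseline, treatment, moderator and their product. The standard error of the continuous slope is about 2 × .777/√92 = .162. At slope .4 the standardised effect is .4/.162 = 2.47 with the score and 2.47 × √.637 = 1.97 with the split, so approximate power is .70 and .50. Simulation (10,000 trials per cell), which also allows for chance variation in the sample, gives slightly lower values:

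| Slope (SD of outcome per SD of moderator) | Continuous | Split |
|---|---|---|
| .2 | .22 | .16 |
| .3 | .43 | .29 |
| .4 | .65 | .46 |
| .5 | .83 | .63 |

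A repeat run agreed to within about .01. With normal errors independent of the regressors, both tests hold the 5% level in this set-up, so the gap does not come from unequal error rates.

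**4. The opposite case.** Suppose the treatment effect jumps by .91 SD exactly at the sample median. The split interaction has standard error 4 × .777/√92 = .324, so the standardised effect is .907/.324 = 2.80. Simulated power is about .78 for the split and .56 for the continuous score.

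**5. How often ties may occur (illustration for CAINS-MAP only).** The protocol says that d = .50 "represents a .36 point difference in means between EnCoRE and control at PT", so the SD of the average rating is .36/.50 = .72. Over nine items that is 9 × .72 = 6.48 points. For a near-normal whole-number score, P(score = median) ≈ Φ(.5/6.48) − Φ(−.5/6.48) = .0615, and 108 × .0615 = 6.6 patients (8.6 at SD 5, 5.4 at SD 8). This applies a planning SD for post-treatment to a baseline score that the entry criterion on the same domain may have reshaped. It shows only that ties are likely.

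**The case against.** **The loss is generic.** The three percentages hold for any median split under linear moderation and are not figures for this trial. That is correct; they are a range under assumed shapes.

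**The true effect may be a step.** The split would then win, as step 4 shows. But nothing in the documents suggests a step, least of all one at this sample's median. This is a reason to check linearity, not to make the split the only analysis.

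**The tests are weak either way.** The protocol says "We have powered this RCT for primary hypotheses 1 and 2 of Specific Aim 2". For the continuous score, 80% power needs a slope of about (1.96 + .84) × .162 = .45. Around a mean effect of .50 SD, that means benefit running from about .05 to .95 SD between patients one SD either side of the mean. At slope .2 both codings usually miss. This stands and limits the importance of the point. It does not favour the coding that discards more.

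**Stronger readings.** A reader might infer that patients at the median were left out of the analysis. The text does not support this: each variable is said to have been dichotomised, so a two-level variable existed, and the reference to above and below may be shorthand. Only the tie rule is unstated. A reader might also infer that the SAP departs from the protocol's modifier model. That model is written for a different set of modifiers and states no coding, so there is no contradiction.

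**Conclusion.** The point holds as a weakness in an exploratory analysis. The SAP's only moderator analysis uses a median split with no rationale and no tie rule. If moderation is graded, the split loses roughly a quarter to a half of the information across the assumed shapes. For a normal moderator with 92 evaluable patients, power falls by about .06 at slope .2 and by about .2 at slopes .4 to .5.

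These figures rest on linear moderation, assumed slopes and a single-time-point ANCOVA with no therapy-group effect, so they indicate size rather than the exact power of the SAP's mixed model. If the moderation is a step at the median, the ordering reverses.

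A reader might infer that the primary results or the sample size are in doubt. They are not: the primary treatment comparisons do not use the moderators. The change is worth making because it is cheap, not because a main conclusion depends on it.

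**What to change.** - Make the continuous, centred moderator-by-treatment-by-time interaction, in the same mixed model, the main moderator test for DAS, SARA-Q and CAINS-MAP.
- Check linearity, for example with a quadratic term, since a step would favour a cut.
- Report each interaction with its 95% confidence interval and label it exploratory. In the simple ANCOVA the half-width at post-treatment is about 1.96 × .162 = .32 SD per SD, so a non-significant test would not show that moderation is absent.
- For display, show treatment effects at the 25th and 75th percentiles of each moderator.
- If the median split is kept, report it as secondary and state which half takes scores equal to the median.
- The SAP is written in the past tense, so disclose this as a re-analysis.

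Cost: a minor code change. Protocol section 5.5 schedules the CAINS, the DAS and a success and resource appraisals questionnaire (taken here to be the SARA-Q) at baseline, so no new data are needed. Downsides: the main test assumes a linear interaction, and a few tests are added to about ten already run without multiplicity adjustment (five moderator-outcome pairs at two time points).
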